	
IVUS Imaging Subset (80 subjects in the Japanese cohort) The IVUS imaging subset of approximately 80 subjects undergo angiography and IVUS assessments at baseline and 12 month follow-up.
 
IVUS + OCT Imaging Subset (20 subjects in the Japanese cohort) The IVUS + OCT imaging subset of approximately 20 subjects undergo angiography, IVUS + OCT assessments at baseline and 12 month follow-up.
 
Single-group study (referred to as PK substudy) Up to 2 de novo lesions located in 2 separate native coronary arteries designated as target lesions may be treated. The PK study will enroll 8 Japanese subjects and is being conducted to assess the blood pharmacokinetics of Sirolimus eluted from the ELX1805J Bioadaptor implanted in patients. PK measurement will be conducted at pre-treatment, 10 minutes, 30 minutes, 1, 2, 4, 6, 12, 24, 72 hours, and 7 days. In addition, all subjects will undergo clinical follow-up assessments at 1, 6 and 12 months and every year for 5 years thereafter.

Enrollment/ Number of Sites	
Approximately 444 subjects will be enrolled at up to 35 centers in Japan and Europe/New Zealand.
 
Planned: Japanese cohort: 222 European/New Zealand cohort: 222 PK substudy: 8

Study Devices	
Investigational device: ELX1805J (Japan); DynamX Sirolimus Eluting Coronary Bioadaptor System (Europe/NZ)
 
Control device: Resolute Onyx Zotarolimus Eluting Coronary Stent System (Medtronic Japan Co., Ltd. or Medtronic per the applicable geography)
 
PK study: Subjects are to receive the ELX1805J device

Clinical Endpoints:	
Primary Endpoint: Target lesion failure (TLF) assessed at 12 months. TLF is a composite endpoint defined as cardiovascular death, target-vessel MI, and clinically-indicated target lesion revascularization (CI-TLR)
 
Secondary Endpoints: Efficacy endpoints
 
 • Acute success rates: Lesion success rate, device success rate, procedure success rate

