	
Clinical endpoints
 
Measured at 30 days, 6 months, 12 months, 2, 3, 4 and 5 years:
 
 • TLF • Patient Oriented Clinical Endpoint: Overall cardiovascular outcomes from the patient’s perspective. This endpoint is a composite endpoint that includes all-cause mortality (cardiac and non-cardiac), stroke, MI (target vessel and non-target vessel) and revascularization (target vessel and non-target vessel) • A composite of all-cause mortality, MI (target vessel or non-target vessel) and revascularization (target vessel or non-target vessel) • Composite of cardiovascular death, target vessel myocardial infarction (TV-MI)*, or clinically-indicated target vessel revascularization (CI-TVR) • Composite of cardiovascular death, stroke, MI (target vessel or non-target vessel) and revascularization (target vessel or non-target vessel) • Composite of cardiovascular death, MI (target vessel or non-target vessel) and revascularization (target vessel or non-target vessel) • Clinically-indicated target lesion revascularization (CI-TLR)TLR • Target vessel revascularization (TVR) • Clinically-indicated TVR (CI-TVR) • Revascularization (target vessel or non-target vessel) • Q-wave MI • Non Q-wave MI • MI (target vessel or non-target vessel) • Target vessel MI • Cardiovascular death • All-cause death • Composite of cardiovascular death or target vessel MI • Composite of all-cause death or MI(target vessel or non-target vessel) • Composite of all-cause death, MI(target vessel or non-target vessel), or TVR • Composite of probable or definite stent thrombosis‡ • Probable stent thrombosis‡ • Definite stent thrombosis‡ 
* Defined as myocardial infarction not clearly attributed to a non-target vessel
 
‡ Defined as per the Academic Research Consortium (ARC-2) criteria

Imaging Endpoints
	
QCA endpoints:
 
 • Acute recoil • Late lumen loss (in-stent and in-segment) at 12-month follow-up

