	
Additional Exclusion Criteria for PK study
 
 • Patients with following criteria 
 ○ Patient with PCI within 180 days before study procedure ○ Patient with plan to have staged PCI within 90 days after study procedure ○ Patients who have non-target lesion

Statistical Methods
	
The analysis of primary endpoint and secondary endpoints are performed using the Intention-To-Treat (ITT) population. The analysis of secondary clinical endpoints are conducted with the Per-Treatment Evaluable (PTE) population in addition to the ITT population.
 
Analysis of the Primary Endpoint
 
Study success is defined as successful rejection of the null hypothesis for the primary endpoint. The primary endpoint for the study is TLF at 12 months post treatment. The primary endpoint will be evaluated using the ITT population for study success and may also be carried out on the PTE population. The null hypothesis for this study is that the ELX1805J arm will have a 12-month TLF rate that exceeds that of the control device arm by at least a pre-specified margin of 6 (delta). The alternative hypothesis is that the ELX1805J arm will have a 12-month TLF rate that is no more than that of the control device, or exceeds that of the control device but by less than 6. Rejection of the null hypothesis will signify that the ELX1805J is non-inferior to the control device with regard to 12-month TLF. The null hypothesis (Ho) and the alternative hypothesis (Ha) can be expressed as below:
 
Ho: $\pi_A \geq \pi_C + 8.6\%$
 
Ha: $\pi_A < \pi_C + 8.6\%$
 
Here, π_A is a true TLF Rate of investigational device, and π_C is a true TLF Rate of control device.
 
Based on non-inferiority test for an endpoint that follows binomial distribution, in addition to difference between TLF rates at 12 months for 2 groups (investigational device - control device), one-sided 95% confidence interval of the difference in TLF is

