calculated. Tests are conducted using normal approximation of binomial distribution. When the upper limit of this confidence interval is less than 8.6% (delta of non-inferiority), the null hypothesis is rejected, confirming non-inferiority of investigational device compared to control device for TLF rate at 12 months. This primary analysis will be conducted using the ITT population. Handling of missing data is described in section 3.4.1. In addition, Kaplan-Meier curve for time till first event considered to be TLF will be done. If multiple TLF occurred in same case, occurrence date of the first TLF is the occurrence date of TLF. During study procedure, up to 2 lesions in different epicardial vessels may be treated with the assigned study device. When there are multiple TLF, in a single case, it is counted per case (counted as single incidence).

Analysis of the Secondary Endpoints

Time-dependent response variables can be expressed using Kaplan-Meier curve, and differences in these variables between groups are tested using log-rank test. Data for all categorical endpoints (e.g., TLF rate at a specific time point, etc.) are shown with number of patients, percentage and Clopper-Pearson's exact 95% confidence interval. Differences between treatment groups are shown using 95% confidence interval of the difference. Comparison of imaging corelab endpoints (QCA, IVUS and OCT) in the Japanese cohort will also use the difference between treatment groups and the 95% confidence interval of the difference. Analyses of clinical secondary endpoints are conducted with the PTE population in addition to the ITT population.

Sponsor

Elixir Medical Corporation
 [name]
 [name]
 USA

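### Is it a defect that the PTE analysis of 12-month TLF is optional as a primary analysis but required as a secondary one?

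*Combined protocol and SAP*

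**What the plan says.** The Clinical Endpoints row gives the primary endpoint as "Target lesion failure (TLF) assessed at 12 months". TLF is also the first item in the secondary list, which is headed "Measured at 30 days, 6 months, 12 months, 2, 3, 4 and 5 years". TLF at 12 months therefore appears under both headings.

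On populations, Statistical Methods opens with a general rule for the secondary endpoints: "The analysis of secondary clinical endpoints are conducted with the Per-Treatment Evaluable (PTE) population in addition to the ITT population". Analysis of the Secondary Endpoints repeats it: "Analyses of clinical secondary endpoints are conducted with the PTE population in addition to the ITT population". For the primary endpoint, Analysis of the Primary Endpoint is permissive: "The primary endpoint will be evaluated using the ITT population for study success and may also be carried out on the PTE population".

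On success, the same section says "Study success is defined as successful rejection of the null hypothesis for the primary endpoint" and, after the decision rule, "This primary analysis will be conducted using the ITT population". The rule is that the upper one-sided 95% limit for the difference (investigational minus control) must be below 8.6%.

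For secondary endpoints the plan gives a per-group exact 95% interval and adds: "Differences between treatment groups are shown using 95% confidence interval of the difference". It attaches no margin and does not state sidedness.

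**The concern.** In a non-inferiority trial, departures from assigned treatment can draw the ITT arms together. An on-treatment analysis is the usual check that an ITT claim does not rest on that. The Study design row says the pooled cohorts are the pivotal evidence for approval in Japan, so the check has some weight.

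Read quickly, the plan leaves it loose in three ways:

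- The PTE analysis of 12-month TLF is optional under one heading and required under another.
- The primary route uses a one-sided 95% limit. The secondary route uses a 95% interval of unstated sidedness, so the two could give different upper limits from the same data.
- The synopsis does not say whether a PTE limit is compared with the margin, or how an ITT pass with a PTE miss should be read.

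If this were a real gap, the choice of whether to hold the PTE result against the margin, and by which limit, could be made after the data were seen.

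**Working it through.** **The passages side by side**

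| | Primary heading | Secondary heading |
|---|---|---|
| Quantity | 12-month TLF difference | 12-month TLF difference |
| Analysis | Non-inferiority test | Descriptive estimate with interval |
| Limit | Upper one-sided 95% | 95% interval, sidedness unstated |
| Compared with 8.6%? | Yes | No |
| ITT | Required, decides success | Required |
| PTE | Permitted | Required |

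The quantity is shared but the analyses differ. An optional test beside a required descriptive display is not a contradiction.

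**How much the choice of limit could matter**

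The plan states no PTE figure to reproduce, so this is an illustration. Inputs from the plan: 444 subjects in two cohorts of 222, allocated 1:1, hence 444/2 = 222 per arm pooled; margin 8.6%; normal approximation. Event counts, control rates and PTE sizes are assumed.

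Upper limit = d + z × √[pA(1−pA)/n + pC(1−pC)/n], with z = 1.645 (one-sided 95%) or 1.960 (two-sided 95%).

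1. 22 versus 13 events at 222 per arm: pA = 9.91%, pC = 5.86%, d = 4.05 points, SE = 2.55 points. One-sided: 4.05 + 1.645 × 2.55 = 8.25%. Two-sided: 4.05 + 1.960 × 2.55 = 9.05%. The two limits straddle 8.6%.

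2. Largest observed difference whose limit stays below 8.6% (222 per arm):

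| Assumed control rate | One-sided | Two-sided |
|---|---|---|
| 3% | 5.05 points | 4.48 points |
| 6% | 4.34 points | 3.62 points |
| 9% | 3.75 points | 2.91 points |

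3. Chance of landing between the two limits if the true rates are equal, by exact binomial enumeration at 222 per arm: 0.1% at a 3% rate, 1.8% at 6%, 4.9% at 9%.

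**ITT and PTE near the margin**

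4. 21 versus 11 events at 222 per arm: d = 4.50 points, SE = 2.445 points, one-sided limit 8.53%, which passes.

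5. The same events with 5% of each arm removed (211 per arm): d = 4.74 points, SE = 2.567 points, limit 8.96%, which misses.

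6. The same observed rates as in step 4 at 211 per arm: d = 4.50 points, SE = 2.445 × √(222/211) = 2.508 points, limit 4.50 + 1.645 × 2.508 = 8.63%, which also misses although the estimated effect is unchanged.

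A PTE miss after an ITT pass is therefore possible near the margin. Step 6 shows that it can come from lost precision alone.

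**The case for a change.** The best case for a change is that it is cheap. Two or three sentences would make the PTE analysis a definite supportive analysis with the same one-sided limit and margin as ITT, and would say in advance how disagreement is reported. It needs no new data. Steps 1 and 5 show that both the choice of limit and modest exclusions can move a result across 8.6%.

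The arithmetic stands, and so does the observation that a PTE margin test is left to discretion. Three things limit what follows:

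- The straddling example applies a threshold that the plan does not apply to the secondary interval. The plan writes one-sided where it means that, so an unqualified 95% interval in a descriptive section is ordinarily read as two-sided.
- Whichever limit is preferred, the PTE estimate and its interval are already required output. A reader can compare them with the margin, so leaving out the formal PTE test does not hide the result.
- A rule that forbids calling the populations consistent whenever the PTE limit misses the margin would be a poor one. By step 6 it could be triggered with an identical estimated effect.

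The text available is a synopsis that points to a fuller section for missing data and does not itself define PTE. The absence of a rule for reading disagreement is shown only for that text.

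**Conclusion.** The concern does not call for a change. The plan permits a PTE repeat of the margin test and requires a descriptive PTE display of 12-month TLF; the two can both be followed as written. ITT alone decides success, so an ITT pass with a PTE miss is a formal success, and the ITT error rate is the same whether the PTE repeat is optional or mandatory. What remains open is the wording of a supportive comparison, which analysts would ordinarily settle by using the primary limit and margin and listing the PTE exclusions by arm and reason.

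The scope for confusion over sidedness is small: a 0.1% to 4.9% chance of falling between the two limits, assuming equal true rates of 3% to 9%, 222 per arm and the 8.6% margin. The size of the PTE population is not given, so the probability of ITT and PTE disagreeing cannot be estimated.

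The primary section also states a margin of 6 in its narrative, against 8.6% in the hypotheses and decision rule. That is a separate and more consequential matter. It would need to be reconciled before any PTE comparison with the margin, but it does not bear on whether the PTE repeat should be optional.

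### Does the plan set two different non-inferiority margins for 12-month TLF, 6 and 8.6%?

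*Combined protocol and SAP*

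**What the plan says.** All the relevant text is in the Statistical Methods row of the synopsis, under Analysis of the Primary Endpoint.

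- **Prose hypotheses.** The null is that the investigational arm's 12-month TLF rate is above control "by at least a pre-specified margin of 6 (delta"). The alternative is that the rate is no higher than control, "or exceeds that of the control device but by less than 6". Neither statement carries a unit.
- **Formal hypotheses.** The prose is then restated in symbols, with Ho: π_A ≥ π_C + 8.6% and Ha: π_A < π_C + 8.6%.
- **Decision rule.** The plan calculates a "one-sided 95% confidence interval of the difference in TLF is" and uses a normal approximation to the binomial. It then states: "When the upper limit of this confidence interval is less than 8.6% (delta of non-inferiority), the null hypothesis is rejected".

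Study success is defined as rejecting this null hypothesis in the ITT population. The two cohorts are pooled, about 444 subjects randomized 1:1, which is 222 per arm.

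**The concern.** Read literally, one paragraph gives two values for the same quantity: 6 in the words and 8.6% in the formulas and the rule. The margin is the threshold for the only confirmatory test, and the pooled data are meant as the pivotal evidence for approval in Japan. If 6 meant 6 percentage points, an upper limit between 6% and 8.6% would satisfy the rule but not the prose. Testing at 8.6% would then also fail to hold a one-sided 5% error rate against a true excess of 6 points. Either would be serious in a pivotal trial, so the text deserves a close check.

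**Working it through.** **Step 1. Set the five statements of the margin side by side.**

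| Place | Value as extracted | Unit | Link to delta |
|---|---|---|---|
| Prose null | 6 | none | the word delta in brackets directly after it |
| Prose alternative | 6 | none | same position in the sentence |
| Formal Ho | 8.6% | yes | restates the prose null |
| Formal Ha | 8.6% | yes | restates the prose alternative |
| Decision rule | 8.6% | yes | named as the delta of non-inferiority |

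Every margin with a unit is 8.6%. Every margin without a unit is the single character 6. The percent signs on 8.6 (three times) and on the 95% confidence levels survived extraction, so it would be odd for a genuine 6% to lose its sign twice and only here. A unitless 6 is also not a possible margin for a difference of two proportions. To become a rival margin it must be given a unit that the text does not supply.

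**Step 2. Put the symbol δ in place of the character.** The null becomes an excess of at least a pre-specified margin of δ (delta). The alternative becomes an excess of less than δ. The formulas then insert the value, and the rule names it: δ = 8.6%. This is the usual order of symbol, gloss and value, and nothing is left to reconcile.

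**Step 3. What the contradiction would amount to if 6 meant 6 percentage points.** Inputs: 222 per arm, no dropout, one-sided 95% limit, z = 1.645. Control rates are assumed, because the available text gives none.

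Upper limit = (p_T − p_C) + 1.645 × √[p_T(1−p_T)/222 + p_C(1−p_C)/222].

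- With 16 control events (7.2%) and 22 test events (9.9%), the difference is 2.70 points and the limit is 2.70 + 1.645 × 2.65 = 7.07%. That is below 8.6% and above 6%.
- With 9 control events, 14 test events give a limit of 5.71% and 19 give 8.28%. So 15 to 19 test events would pass at 8.6% and fail at 6%.
- The chance that the 8.6% rule passes at a true excess of 6 points is Φ[(0.086 − 0.06)/SE − 1.645]. At control 5%, SE = √[(0.05×0.95 + 0.11×0.89)/222] = 0.0256, so Φ(1.016 − 1.645) = 26.5%. Exact enumeration gives 27.7% there, and 36.9%, 30.1% and 25.8% at control 2%, 4% and 6%.

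This arithmetic is correct, but all of it depends on a 6-point margin existing. With δ = 8.6%, the result with 16 and 22 events is simply non-inferior (7.07% < 8.6%).

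**Step 4. Does the sample size show which margin was planned?** No expected TLF rate, power or dropout accompanies the 444 in the available text, so that number cannot be reproduced. Solving n = 2p(1−p)(1.645 + z_power)²/margin² for a common rate p gives:

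| n per arm | Margin | p at 80% power | p at 90% power |
|---|---|---|---|
| 222 | 8.6% | 15.8% | 10.7% |
| 222 | 6% | 6.9% | 4.9% |
| 111 (one cohort) | 8.6% | 7.2% | 5.0% |

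Several combinations are possible, so the size does not identify the margin. With 8.6% and 222 per arm, power at equal true rates of 5%, 7% and 10% is 99.4%, 97.2% and 91.5%. The pooled size is therefore ample for the stated rule over that range.

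**The case for a change.** The strongest case for a real 6 has three parts.

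1. The extraction rendered π correctly in the formulas of the same section, so it could have rendered δ. This is weak: those symbols are set as formulas, the 6 sits in running prose, and π does not resemble a digit.
2. The decision rule itself puts a number before a bracketed mention of delta, so a literal number in that position would not be out of style. True, but that number has its percent sign and the 6 does not.
3. A 6% margin for the pooled trial fits numerically. Precision scales with √n, and 8.6/√2 = 6.08, so 6% with 222 per arm and 8.6% with 111 per arm imply nearly the same TLF rate (6.9% and 7.2% at 80% power). This is the best of the three. It makes 6% conceivable, but nothing in the text says that the margin was rescaled for pooling, and both formal hypotheses and the rule say 8.6%.

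What stands is that a printed digit cannot be ruled out without the original page. If the page did show one, the sponsor would have to reconcile the prose with Ho, Ha and the rule and add the unit. That would still not create a second test: no rule compares the limit with 6, and an upper limit below 8.6% is what rejects the null. Nor could it be said that a stated power would worsen, because the available text states none.

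**Conclusion.** The concern does not hold. The most natural reading is a lower-case delta misread as a 6 during text extraction, which is not a fault of the plan. On that reading, the margin for 12-month TLF is 8.6 percentage points throughout, and study success has one threshold: a one-sided 95% upper limit below 8.6%. The size of the discrepancy is then zero, and neither the zone of opposite verdicts nor the inflated error rates arise.

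The conclusion rests on the wording: the missing unit in both places, the bracketed gloss, and the restatement of the same hypotheses with 8.6%. It does not rest on the sample size, which is uninformative here. A look at the original page would settle the remaining doubt. In either case, a sponsor following the written decision rule applies 8.6%.

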Study design	
A prospective, multicenter, randomized (1:1; DynamX Bioadaptor (ELX1805J): Resolute Onyx), single-blind study, registering approximately 444 subjects at approximately 35 sites within Japan, Europe, and New Zealand to be conducted in two parallel cohorts. The combined Japan Bioadaptor RCT data and European Bioadaptor RCT data are intended to serve as the pivotal trial to support the regulatory approval in Japan with the Pharmaceuticals and Medical Devices Agency (PMDA).
 
Up to 2 de novo lesions located in 2 separate native coronary arteries designated as target lesions may be treated. The target lesion(s) must measure between 2.25 mm and 4.0 mm in diameter and ≤ 34 mm in length, to be covered by a single ELX1805J Bioadaptor or a single control device. Patients should not be randomized until after satisfactory pre-dilatation of the target lesion has been performed.
 
A non-target lesion may be treated if located in separate epicardial vessel (RCA, LCX or LAD) using an approved ‘olimus drug eluting stent provided the treatment of this non-target lesion is done prior to the treatment of the target lesion(s), and the treatment of the non-target lesion is considered successful. The segment should be located such that any injury that might occur during intervention can be clearly attributable to that treated segment.
 
Japanese Cohort (222 subjects) & European/New Zealand Cohort (222 subjects) The study is composed of two cohorts, i.e., the Japanese cohort and the European/New Zealand cohort. For each cohort, at least 222 subjects are randomly allocated in a 1:1 ratio to either the test or control arm. All subjects will receive follow-up clinical assessments at 1, 6 and 12 months and every year for 5 years thereafter. Additionally, imaging follow-up with IVUS and IVUS + OCT are collected in the following imaging subsets. Data from the Bioadaptor RCT European Cohort will be pooled with the data from the Bioadaptor RCT Japan Cohort to support primary and secondary endpoints. The primary endpoint analysis will be performed using the Intent-to-Treat (ITT) population on all subjects at the point of randomization.

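### The 2- to 5-year event rates are planned as crude percentages with exact binomial intervals, which withdrawal biases under either usual denominator; Kaplan-Meier or cumulative-incidence estimates would avoid this

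*Combined protocol and SAP*

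**What the plan says.** The Combined protocol and SAP, Statistical Methods, Analysis of the Secondary Endpoints, sets two rules side by side.

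- **Time-to-event rule:** "Time-dependent response variables can be expressed using Kaplan-Meier curve, and differences in these variables between groups are tested using log-rank test".
- **Fixed-time rule:** categorical endpoints ("e.g., TLF rate at a specific time point, etc.) are shown with number of patients, percentage") also receive "Clopper-Pearson's exact 95% confidence interval". For the contrast, "Differences between treatment groups are shown using 95% confidence interval of the difference".

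The example given for the second rule is itself a TLF rate at a time point. The list of secondary clinical endpoints is headed "Measured at 30 days, 6 months, 12 months, 2, 3, 4 and 5 years", so the fixed-time rule reaches the 2-, 3-, 4- and 5-year rates. Follow-up matches: "All subjects will receive follow-up clinical assessments at 1, 6 and 12 months and every year for 5 years thereafter".

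The public text gives no denominator for these percentages and no rule for subjects who leave before the time point. The paragraph on the primary endpoint refers to section 3.4.1 for missing data, but that section is not in the public text.

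**The concern.** A binomial percentage presumes that every subject's status is known at the time point. Over five years some subjects will withdraw or be lost, and each usual denominator then errs in a fixed direction:

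- **All randomised subjects:** a subject who leaves event-free is counted as event-free at 5 years, so the rate is too low.
- **Evaluable subjects (event, or followed to the time point):** early events stay in while event-free leavers drop out, so the rate is too high.

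Naming one of these denominators therefore does not remove the bias. If withdrawal differs between arms, the arm difference is biased as well. The trial would also report two 5-year TLF figures, one read from its Kaplan-Meier curve and one from its table. They would disagree, and nothing says which prevails.

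**Working it through.** The documents give no long-term event rate and no dropout rate, so there is no stated figure to reproduce. All rates below are assumptions. From the documents come only the horizon (5 years) and the size (444 randomised 1:1, about 222 per arm).

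**1. Withdrawal only.** Assume a true 5-year TLF of 12%, constant hazards, and exits independent of risk.

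- Event hazard: λ = −ln(0.88)/5 = 0.02557 per year. The exit hazard is μ.
- Still followed and event-free at 5 years: S = exp(−5(λ+μ)).
- All-randomised percentage: C = λ/(λ+μ) × (1 − S).
- Evaluable percentage: E = C/(C + S).
- Left event-free: 1 − C − S.

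| μ per year | S | Left event-free | C | E | Truth |
|---|---|---|---|---|---|
| 0.01 | 83.71% | 4.6% | 11.71% | 12.27% | 12% |
| 0.03 | 75.74% | 13.1% | 11.16% | 12.84% | 12% |
| 0.05 | 68.53% | 20.8% | 10.65% | 13.45% | 12% |

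Under these assumptions Kaplan-Meier targets 12% in every row. Replacing 5 by 2 in the formulas, with μ = 0.03, gives C = 4.84% and E = 5.13% against a true 4.98%, so the bias is much smaller at 2 years.

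**2. Unequal withdrawal, equal true TLF.** Take μ = 0.01 in one arm and 0.05 in the other.

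- All randomised: 11.71 − 10.65 = about 1.1 points. The arm with more exits looks better.
- Evaluable: 13.45 − 12.27 = about 1.2 points. The arm with more exits looks worse.

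A milder case assumes a 10% event probability, 5% other-cause death in both arms, and withdrawal of 5% against 15%. The false difference is then about 0.5 points (all randomised) or 0.6 points the other way (evaluable, with the dead dropped).

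**3. Other-cause death only.** Put a death hazard δ = 0.01 in place of withdrawal. TLF is defined thus: "TLF is a composite endpoint defined as cardiovascular death, target-vessel MI, and clinically-indicated target lesion revascularization (CI-TLR"). Non-cardiovascular death is therefore outside it and competes with it.

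- True cumulative incidence: λ/(λ+δ) × (1 − exp(−5(λ+δ))) = 11.71%.
- Events over all randomised: 11.71%, so no bias.
- Events over a denominator that drops the dead: 0.1171/(0.1171 + 0.8371) = 12.27%, too high.
- One minus Kaplan-Meier with deaths censored: 1 − exp(−5λ) = 12.0%, also too high.

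**4. Effect on the intervals.** Summing binomial probabilities over all counts whose Clopper-Pearson interval contains 12%, coverage at μ = 0.03 is about 93.6% for all randomised (n = 222). It is about 93.8% for evaluable subjects (n = 222 × (0.1116 + 0.7574) ≈ 193). At these rates a single-arm interval loses little. For scale, the 95% half-width of an arm difference at 12% is 1.96 × √(2 × 0.12 × 0.88/222) = 6.0 points.

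**The case against.** The strongest reply is that the plan already contains methods that handle censoring. Kaplan-Meier curves are foreseen, and the only between-arm test named for time-dependent secondary endpoints is the log-rank test. No hypothesis, margin or success criterion is attached to any 2- to 5-year rate. The bias is around one point under assumed exit rates, against a half-width of about six points for the arm difference. The 1.1 to 1.2 point difference needs a five-fold contrast in exit rates, and nothing in the documents predicts that. All of this stands, and it limits the point to the late descriptive rates, their intervals and their differences. It does not remove the point, because the text does not take those three quantities from the curves.

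A reader might also infer more than the documents support:

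- **That deaths from other causes bias the percentage under either denominator.** Step 3 shows otherwise. With all randomised subjects as denominator and no withdrawal, the crude percentage is the correct cumulative incidence. Death does harm only if the dead are dropped, or if they are censored in a plain Kaplan-Meier estimate. Endpoints that include all-cause death have no competing death.
- **That the plan has no missing-data rule for late endpoints.** Section 3.4.1 is not in the public text and could contain one, such as imputation or censoring. The supportable statement is that the public text shows none for these percentages.
- **That the primary conclusion is at risk.** Study success depends on TLF at 12 months, and this point does not touch that test.

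**Conclusion.** The point holds for withdrawal and is a cheap improvement. Following the fixed-time rule as written gives late rates that are too low or too high, depending on the denominator. The error is about 0.8 points either way at assumed exits of 3% per year with a true 5-year TLF of 12%. At 5% per year it is about 1.4 points, and at 2 years it is far smaller. The arm difference is biased only if withdrawal differs by arm, by about 0.5 to 1.2 points in the scenarios shown.

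These sizes rest on constant hazards, on exits unrelated to risk, and on event and exit rates that the documents do not give. The direction of each bias does not depend on the particular rates, provided that leavers remain at risk and leave independently of that risk. If section 3.4.1 already sets a censoring or imputation rule for the late endpoints, the point reduces to a cross-reference.

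**What to change.** For the clinical endpoints at 2, 3, 4 and 5 years, add to Analysis of the Secondary Endpoints:

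- **Endpoints that include all-cause death:** take the rate from the Kaplan-Meier estimate, with a 95% interval from the Greenwood variance on the log-log scale.
- **All other endpoints** (for example TLF, CI-TLR, target-vessel MI, stent thrombosis): take the rate from the Aalen-Johansen cumulative incidence, with deaths that are not part of the endpoint as the competing event, and its matching 95% interval.
- **Arm difference:** the difference of these two estimates, with a 95% interval from their combined standard errors.
- **Crude counts:** keep them as description, with the denominator stated and the numbers withdrawn or lost shown by arm at each time point. These numbers also let a reader judge whether exits look unrelated to risk, which the new estimates still assume.

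The cost is SAP wording and a little more analysis work with standard procedures. No new data are needed. The intervals become slightly wider than binomial ones computed on all randomised subjects.
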